7 ADVERSE EVENTS

Investigators are responsible for monitoring the safety of patients who have entered this study and for alerting the Principal Investigator to any event that seems unusual, even if this event may be considered an unanticipated benefit to the patient.

The Investigator is responsible for appropriate medical care of patients during the study. The Investigator remains responsible to follow, through an appropriate health care option, AEs that are serious or that caused the patient to discontinue before completing the study. The patient should be followed until the event resolves or is explained.

7.1 Definitions

7.1.1 Adverse Events (AEs)

An AE is any untoward medical occurrence in a patient or trial patient following administration of a drug or biologic (medicinal product) or using a medical device and that does not necessarily have a causal relationship with that treatment or usage.

Any unfavourable and unintended sign (including an abnormal laboratory finding), symptom, or disease temporally associated with the use of a medical treatment or procedure regardless of whether it is considered related to the medical treatment or procedure (attribution of unrelated, unlikely, possible, probable, or definite).

Each AE is a unique representation of a specific event used for medical documentation and scientific analysis.

7.1.2 Serious Adverse Events (SAEs)

A Serious Adverse Event (SAE) is any untoward medical occurrence that:

- Results in death;
- Is life-threatening;
- Results in inpatient hospitalization or prolongation of existing hospitalization;
- Results in persistent or significant disability/incapacity;
- Results in congenital anomaly/birth defect;
- Is medically significant in the opinion of the Investigator.

A life-threatening AE is defined as any adverse experience that places the patient at immediate risk of death from the reaction as it occurred; i.e., it does not include a reaction that, had it occurred in a more severe form, might have caused death.

Hospitalization is defined as any inpatient admission (even if less than 24 hours) as a result of a precipitating, treatment-emergent AE. Hospitalizations for administrative reasons or a non-worsening pre-existing condition should not be considered AEs (e.g., admission for workup of a

Clinical Study Protocol, Study No AVP0458-01-001, Amendment 4, 23rd October 2012 Page 36 of 46

persistent pre-treatment lab abnormality, yearly physical exam, protocol-specified admission, elective surgery). Pre-planned treatments or surgical procedures should be noted in the baseline documentation. However, if a hospitalization due to an unknown event occurs, other than for elective admissions for pre-existing conditions, it should be considered as a SAE. Hospitalization for reasons of disease progression is not considered a SAE.

Prolongation of hospitalization is defined as any extension of an inpatient hospitalization beyond the stay anticipated/required for the original reason for admission, as determined by the Investigator or treating physician.

Disability is a substantial disruption of a person's ability to conduct normal life functions.

An AE that is not fatal, life-threatening, or requires hospitalization may be considered medically significant and therefore serious when, in the opinion of the Investigator, it could jeopardize the patient and may require medical or surgical intervention to prevent any of the above outcomes. Examples of such medical events include allergic bronchospasm requiring intensive treatment in the emergency room or at home, blood dyscrasias that do not result in inpatient hospitalization, or the development of drug dependency or abuse.

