5.9 Safety Monitoring and Management

5.9.1 Infusion Safety Monitoring

On the day of ¹²⁴I-PEG-AVP0458 infusion, all patients will have baseline vital signs taken prior to the infusion. Saturated solution of Potassium Iodide (SSKI) (obtained from Hospital pharmacy), 10 drops twice daily, will be administered immediately prior to the infusion and will continue for a total of 10 days. All concomitant therapies and ongoing AEs occurring since the last visit will be reviewed and documented in the patient's medical history and eCRF.

For the infusion, vital signs and careful monitoring for symptoms such as allergic reactions will be measured and recorded during the infusion and the 4 hours post infusion completion. Vital signs and all AEs occurring during this period will be documented in the patient's medical history and eCRF.

All Grade 2 and higher AEs occurring during the infusion and up to 4 hours post-infusion are considered to be infusional toxicities regardless of relationship to drug and CTCAE v4.0 Grade.

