6.1 Safety Evaluation

Safety of ¹²⁴I-PEG-AVP0458 will be determined by the ongoing monitoring of the incidence and intensity of AEs graded using the National Cancer Institute Common Terminology Criteria for Adverse Events (CTCAE) v4.0 (Appendix 2), with special emphasis on DLT events and infusional toxicities. A copy of CTCAE v4.0 also may be downloaded from the Cancer Therapy Evaluation Program home page (http:\\ctep.info.nih.gov).

A DLT is defined as any of the following events occurring within 30 days of study drug administration:

- Any Grade 2 or greater allergic reaction.
- Any Grade 3 toxicity. Exceptions are: fever; asymptomatic hyperglycemia; hypophosphatemia; nausea, vomiting, or diarrhoea despite the use of optimal supportive medical therapy; leukopenia or thrombocytopenia that revert to baseline within three weeks of occurrence; lymphopenia without other dose-limiting events (eg opportunistic infection).
- Any Grade 4 toxicity.

To be dose-limiting, a toxicity must be possibly, probably, or definitely related to the administration of ¹²⁴I-PEG-AVP0458. All DLTs must be discussed with the study Coordinating Principal Investigator.

AEs will be collected after the patient has been enrolled. AEs occurring after signing informed consent but prior to receiving study drug (ie before enrolment) should only be reportable if related to study procedures. All AEs occurring after enrolment must be recorded until 30 days following the end of treatment exposure. Refer to Section 7.2.1. AEs include adverse drug reactions, any unfavourable sign or symptom (related and unrelated), illnesses with onset during the study, or exacerbations of pre-existing illnesses or conditions. Progression of the patient's malignancy should not be considered an AE, unless, in the Investigator's opinion, study treatment resulted in an exacerbation of the patient's condition. Exceptions are if disease progression results in death or hospitalization while on study or within 30 days of the last dose. If either occurs, progressive disease will be reported as a SAE (see Section 8.2.2) and will also be documented on an AE eCRF. All observed or volunteered AEs, regardless of treatment group or suspected causal relationship to study drug, will be recorded on the AE eCRF.

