7.2.2 Serious Adverse Events (SAEs)

After becoming aware that an SAE has occurred, all sites must report it to the Sponsor or designee within 24 hours of awareness of the event, regardless of suspected relationship to study drug. Sites will be provided with contact information for SAE reporting before enrolling their first patient.

The initial report should include at minimum the following information: patient number and initials, sex, age; event term; and Investigator's preliminary assessment of causality. Follow-up information including causality, severity, outcome, action taken, and concomitant medications should be communicated to the Sponsor immediately.

Any SAE or death must be reported immediately regardless of the circumstances or suspected cause if it occurs or comes to the attention of the Investigator any time a patient is on study (as soon as the informed consent has been signed) or within 30 days of study drug

Clinical Study Protocol, Study No AVP0458-01-001, Amendment 4, 23rd October 2012 Page 37 of 46

administration. Any SAE or death occurring more than 30 days after drug administration must be reported if a causal relationship to study drug is suspected.

It is the Investigator's responsibility to notify the Ethics Committees of all SAEs that occur at his or her site.

Study site personnel must fax the completed SAE form(s) within one working day to Medpace Serious Adverse Event Reporting [contact]. Attach a photocopy of all examinations carried out and the dates on which these examinations were performed. For laboratory results, include the normal ranges.

Type of Event	Reporting Time to	Reporting Time to TGA	Type of Report
	Designee by Site		
Fatal or Life-threatening	Within 24 hours	Within 7 calendar days	Initial report
	Within 7 days	Within 8 additional	Complete report
		calendar days	
All Other Serious	Within 24 hours		Initial report on SAE
			Report – Form
	Within 7 working days	Within 15 calendar days	Updated information
			on the original SAE
			Report - Form
Non-serious	Per eCRF submission		AE Report - Form
	procedure		

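### Sections 6.1 and 7.1.2 give opposite answers on whether hospitalisation for disease progression is a serious adverse event, so the SAE count depends on which section a site follows

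*Protocol*

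**What the plan says.** Protocol Section 7.1.2 lists inpatient admission among the criteria for a serious adverse event and then carves out one cause: "Hospitalization for reasons of disease progression is not considered a SAE". It attaches no time limit or exception to that sentence.

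Protocol Section 6.1 starts from the position that progression of the malignancy is not an adverse event unless the investigator thinks study treatment made the condition worse. It then adds: "Exceptions are if disease progression results in death or hospitalization while on study or within 30 days of the last dose". The consequence follows at once: "If either occurs, progressive disease will be reported as a SAE (see Section 8.2.2) and will also be documented on an AE eCRF".

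Section 8.5 (Primary Safety Assessments) names three adverse event summaries beyond the overall one: serious events, grade 3 or 4 events, and treatment-related events.

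On a lesser point, Section 5.9.1 opens its definition with "All Grade 2 and higher AEs occurring during the infusion and up to 4 hours post-infusion are considered to be infusional toxicities" and closes the same sentence with "infusional toxicities regardless of relationship to drug and CTCAE v4.0 Grade". Section 6.1 monitors safety "with special emphasis on DLT events and infusional toxicities", while Section 8.2.1 places its emphasis on infusion-related adverse events, a different term that is not tied to the 5.9.1 definition.

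**The concern.** Safety is the primary endpoint, and the SAE tally is one of its named outputs. A patient admitted for progression in the weeks after the infusion is an SAE to a site that works from Section 6.1 and not an SAE to a site that works from Section 7.1.2. Two sites infuse patients, so both rules could be applied within one table.

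The adverse event count can move as well. Where the investigator does not blame study treatment, the exception in 6.1 is the only route by which progression becomes an adverse event at all.

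A later analysis plan cannot fully repair this. Sites classify events from the protocol when they occur, and an admission never filed as an SAE may not be recoverable from the database.

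**Working it through.** **The two rules side by side**

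- Event: an inpatient admission for progression, during the study or within 30 days of the single infusion, not attributed to study drug.
- Section 6.1: reported as an SAE and entered on an adverse event eCRF. Count = 1.
- Section 7.1.2: not an SAE. Count = 0.
- Death from progression is not in dispute. The carve-out in 7.1.2 covers admission only, and death is an SAE criterion in its own right.

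**Can one be read as an exception to the other?**

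1. Section 7.2.2 collects SAEs whatever their cause from consent until 30 days after drug administration. After that, only events suspected to be drug-related are reported.
2. The 6.1 exception covers the study period plus 30 days after the last dose, and each patient has one dose.
3. The two windows nearly coincide. If 6.1 prevails, the sentence in 7.1.2 has almost nothing left to govern. If 7.1.2 prevails, the admission half of the 6.1 exception has no effect.
4. Section 6.1 points to 8.2.2 for SAEs, but 8.2.2 is Secondary Endpoints. Section 7.2.2 deals with SAE reporting and does not mention progression. Nothing else in the protocol resolves the conflict.

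**Size**

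The denominator comes from the planned total of 12-18 (Section 3.2). It reproduces from the design: 3 + 3 + 6 = 12 with no cohort expanded, and 6 + 6 + 6 = 18 with both expanded. One reclassified patient with no other SAE moves the patient-level SAE rate by 1/n. Starting from no other SAE, with exact (Clopper-Pearson) 95% intervals:

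- n = 18: 0/18 = 0% (0 to 18.5%) becomes 1/18 = 5.6% (0.1 to 27.3%).
- n = 12: 0/12 = 0% (0 to 26.5%) becomes 1/12 = 8.3% (0.2 to 38.5%).
- Cohort of 3: 0/3 = 0% (0 to 70.8%) becomes 1/3 = 33.3% (0.8 to 90.6%).

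**How likely is at least one such admission?**

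The protocol gives no rate. Assuming a per-patient risk p, independent between patients, the chance is 1 − (1 − p)^n:

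- p = 5%: 46% for n = 12, 60% for n = 18.
- p = 10%: 72% and 85%.
- p = 20%: 93% and 98%.

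These values of p are assumptions. Patients have ECOG status 0-1 and expected survival of about three months or more, and are followed for about four weeks, so the upper end should not be taken as typical.

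**Reach**

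A DLT is defined by grade, type of event and at least possible relatedness (Sections 3.1 and 6.1). Seriousness plays no part. Progression that the investigator attributes to study treatment is an adverse event under 6.1 in any case. The conflict therefore changes no DLT count, and no sample size, power or alpha depends on it.

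**The case against.** The best defence is that 7.1.2 states the general rule and 6.1 a time-limited exception. That does not stand: 7.1.2 makes no reference to 6.1, and the exception would cover nearly all the time in which SAEs are collected.

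It can also be said that the analyses are descriptive, that adverse events are listed by cohort, and that few admissions for progression are likely in four weeks among fit patients. All of that is true. It limits the consequence but does not remove the contradiction.

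A reader might infer three stronger points, which the protocol does not support.

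- **Infusional toxicity is equally contradictory.** The subject of the 5.9.1 sentence is events of Grade 2 and above, so the closing words about grade can be read as redundant. Grade 1 events are recorded and graded as adverse events either way. Nor is infusional toxicity one of the summaries named in Section 8.5. What remains is a clumsy sentence, and a term that differs from the one in 8.2.1.
- **The SAE reporting clock conflicts.** Section 7.2.2 says sites "must fax the completed SAE form(s) within one working day" and also sets 24 hours from awareness. The 24-hour duty to notify stands in both the text and the table and is never lifted. The completed form can be read as a separate, fuller document. Timing changes no count.
- **The main safety results are left undetermined.** Only the SAE summary, and the adverse event entry for the same admissions, depends on the conflict.

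**Conclusion.** The contradiction between Sections 6.1 and 7.1.2 is direct, and nothing in the protocol resolves it. It should be corrected because it affects a named summary of the primary endpoint in a trial where one patient is worth 5.6 points (n = 18) to 8.3 points (n = 12), or 33.3 points in a cohort of three. Those figures assume that the affected patient has no other SAE and that every enrolled patient is in the safety population.

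The finding stops there: escalation by DLT is untouched, and the number of admissions that would be affected is unknown. The protocol does not show which of the two rules was intended, and this review does not choose between them. The sentence in 5.9.1 is a secondary wording note only.

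**What to change.** 1. Decide on one rule for hospitalisation due to progression and write it in the same words in Sections 6.1 and 7.1.2.
2. Replace the reference to 8.2.2 in Section 6.1 with the SAE sections, 7.1.2 and 7.2.2.
3. If progression admissions are included, tabulate progression-related SAEs on their own line, so that the SAE rate can be read with and without them.
4. If patients have already been treated, check admissions to date against the chosen rule.
5. In Section 5.9.1, state once whether Grade 1 events in the infusion window count as infusional toxicities, and use the same term in Section 8.2.1.

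The cost is a few sentences of protocol text, a matching line in the eCRF completion guideline, and at most one extra table row. No sample size or analysis method changes.

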7.2 Reporting Procedures

7.2.1 Adverse Events (AEs)

AEs will be collected after the patient has been enrolled.

If a patient experiences an AE after the informed consent document is signed (entry), but prior to enrolment (assignment to treatment), the event will NOT be reported unless the Investigator feels that the event may have been caused by a protocol procedure.

All AEs occurring after enrolment must be documented in the source records and reported on the eCRF, regardless of the assumption of a causal relationship. Documentation of "AE Summaries" for these AEs is reported to the Sponsor.

Documentation of AEs includes: date of suspected onset and resolution, severity, seriousness, related interventions and outcome. The Investigator must also evaluate the probability of a causal relationship of the AE to the study medication as defined in **Section 7.3**.

7.2.2 Serious Adverse Events (SAEs)

After becoming aware that an SAE has occurred, all sites must report it to the Sponsor or designee within 24 hours of awareness of the event, regardless of suspected relationship to study drug. Sites will be provided with contact information for SAE reporting before enrolling their first patient.

The initial report should include at minimum the following information: patient number and initials, sex, age; event term; and Investigator's preliminary assessment of causality. Follow-up information including causality, severity, outcome, action taken, and concomitant medications should be communicated to the Sponsor immediately.

Any SAE or death must be reported immediately regardless of the circumstances or suspected cause if it occurs or comes to the attention of the Investigator any time a patient is on study (as soon as the informed consent has been signed) or within 30 days of study drug

Clinical Study Protocol, Study No AVP0458-01-001, Amendment 4, 23rd October 2012 Page 37 of 46

administration. Any SAE or death occurring more than 30 days after drug administration must be reported if a causal relationship to study drug is suspected.

It is the Investigator's responsibility to notify the Ethics Committees of all SAEs that occur at his or her site.

Study site personnel must fax the completed SAE form(s) within one working day to Medpace Serious Adverse Event Reporting [contact]. Attach a photocopy of all examinations carried out and the dates on which these examinations were performed. For laboratory results, include the normal ranges.

Type of Event	Reporting Time to	Reporting Time to TGA	Type of Report
	Designee by Site		
Fatal or Life-threatening	Within 24 hours	Within 7 calendar days	Initial report
	Within 7 days	Within 8 additional	Complete report
		calendar days	
All Other Serious	Within 24 hours		Initial report on SAE
			Report – Form
	Within 7 working days	Within 15 calendar days	Updated information
			on the original SAE
			Report - Form
Non-serious	Per eCRF submission		AE Report - Form
	procedure		

7.2.3 Pregnancy Reporting

Any pregnancy that occurs in a study subject or his partner during the study or occurring up to 30 days after the last dose of study medication must be reported. Study site personnel must complete and fax the Exposure in Utero form within one working day to Medpace Clinical Safety [contact].

Follow-up should be documented in source notes and should be continued until final outcome is known. Study site personnel must complete and fax the follow-up Exposure in Utero form to Medpace Clinical Safety when new information or the final outcome of the pregnancy is available.

7.3 Attribution of AEs to Investigational Agent

The relationship of an AE to the investigational agent will be determined by the Investigator on the basis of their clinical judgement, using one of the following terms, as described in the NCI Guidelines

Attribution	Description	
Unrelated	The AE is clearly NOT related to the intervention	
Unlikely	The AE is doubtfully related to the intervention	
Possible	The AE is possibly related to the intervention	
Probable	The AE is likely related to the intervention	
Definite	The AE is clearly related to the intervention	
Clinical Study Prot	cocol, Study No AVP0458-01-001, Amendment 4, 23rd October 2012	Page 38 of 46

7.4 Severity of AEs

All toxicities or adverse experiences will be graded according to NCI CTCAE v4.0 (Appendix 2).

BIOSTATISTICS 8

This is an open-label, non-randomized study of the safety and biodistribution of PEG-AVP0458. The analyses in this trial are descriptive and exploratory.

8.1 Sample Size/Accrual Rate

TAG-72 is expressed in more than 70% of ovarian cancer tumours, and more so in advanced cases [17].

Approximately 80-85% of primary prostate tumours and approximately 50% of metastatic tumours can be expected to overexpress TAG-72, indicating that the patient resource is available for this clinical study [13-15].

An anticipated total of 12-18 patients will be entered into the study. See Section 3.2.

8.2 Primary and Secondary Study Variables

8.2.1 Primary Endpoint

The primary endpoint is to evaluate the safety of a single dose of PEG-AVP0458 in patients with prostrate and ovarian cancer. Safety will be evaluated by adverse events, ECOG performance status, vital signs, 12-lead ECG and laboratory parameters. Adverse events (AEs) will be coded using the standard Medical Dictionary for Regulatory Activities (MedDRA) and grouped by system organ class. AEs will be graded by the investigator according to the NCI-CTCAE (version 4.0). Special emphasis will be considered for any dose limiting toxic adverse event and infusion related adverse events.

8.2.2 Secondary Endpoints

The secondary objectives of this study are to evaluate the biodistribution of ¹²⁴I-PEG-AVP0458. including tumour targeting, dosimetric analysis, PK analysis performed on ¹²⁴I-PEG-AVP0458 serum radioactivity data and serum concentrations of PEG-AVP0458 and immunogenicity of 124I-PEG-AVP0458 in patients with prostate and ovarian cancer.

8.3 Populations

There will be two populations for consideration.

8.3.1 **Safety Analysis Population**

The safety analysis population includes all patients who were administered study drug and have at least one safety assessment after their infusion.

Evaluable Analysis Population

The evaluable analysis population includes patients who were administered study drug and completed the 4 weeks of scheduled assessments after receiving the infusion.

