5.3 Administration of Investigational Product

The appropriate quantities of 124 I-PEG-AVP0458 will be drawn into a syringe with sterile sodium chloride injection and 5% human serum albumin (HSA). The resultant 124 I-PEG-AVP04 in the syringe will be injected into a 100 mL infusion bag of sterile sodium chloride injection and 5% HSA via a sterile 0.2 μ m filter.

Patients will receive 1 mg/m² or 10 mg/m² of ¹²⁴I-PEG-AVP0458 infusion intravenously over approximately 1 hour. Patients will be kept reclined during the infusion and observed for the first four hours after the infusion has been completed.

PEG-AVP-0458 will be labelled with ¹²⁴I in laboratories of the Ludwig Institute of Cancer Research, at Austin Health, under sterile conditions and according to SOPs (see Section 9.3). Following QC testing, the dose of 124 I-PEG-AVP-0458 will be then distributed to the infusion room at the study site for subsequent patient infusion. The criteria for dose escalation and dose selection are provided in Section 5.14.

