5.4 Post-Administration of Investigational Product (Day 0)

The following assessments are undertaken:

- Vital signs (blood pressure, pulse, respiratory and temperature) every 15 minutes during the infusion, at completion of infusion, and at 1, 2 and 4 hours after infusion completion. Note: these time points correspond to 2, 3 and 5 hours after commencement of infusion.
- Blood sample taken immediately post infusion, and then at 1, 2 and 4 hours after completion of infusion for assessments of pharmacokinetics by ELISA and ¹²⁴I counting.
- A PET scan is performed approximately 1 hour after infusion, according to the PET Imaging Charter.
- Adverse events, if observed, are recorded, taking special precaution for anaphylaxis, allergic and/or infusion reactions (see Section 5.9.2).

At the end of the assessments (five hours after commencement of infusion), patients may return home if there are no ongoing adverse effects of the infusion.

5.5 Days 1, 2 or 3, 4 or 5, 6 or 7 (Study Visits 1, 2, 3 and 4 post infusion)

Patients return to the Study Site at the appointed time for the following assessments:

- Vital signs (blood pressure, pulse, respiratory and temperature)
- ECOG performance
- Concomitant medications. Prescription and non-prescription therapies must be documented. Trade or generic name, indication, quantity administered, route, and dates of administration will be listed.
- Adverse events
- Blood sample for assessments of pharmacokinetics by ELISA and ¹²⁴I counting
- Blood sample for assessment of HADA on day 6 or 7
- PET scan

Some flexibility is allowed in the schedule (eg. Day 2 or 3, 4 or 5, 6 or 7) to allow for availability of PET/CT scans and weekends. Such flexibility is enabled by the relatively long half-life of the 124I radionuclide and the diabody being studied.

Clinical Study Protocol, Study No AVP0458-01-001, Amendment 4, 23rd October 2012 Page 28 of 46

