5.13 Patient Evaluability

All patients who receive the infusion of ¹²⁴I-PEG-AVP0458 diabody will be evaluable for safety. Every effort will be made to obtain complete information on all AEs, with particular emphasis on serious AEs, infusional toxicities, and hypersensitivity reactions. Patients will be evaluable for biodistribution and pharmacokinetics assessment if they complete all study procedures up to Visit 4 (Day 6 or 7

visit). Patients will be evaluable for immunogenicity of PEG-AVP0458 if they have completed the Day 28 (±2 days) visit procedures.

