5.14 Criteria and rules for stopping patient treatment

An Investigator may stop a patient's participation for the following reasons:

- The patient withdraws consent.
- The patient is no longer able to participate.
- A patient can be withdrawn after discussion between the Sponsor and Investigator if eligibility criteria are violated or if the patient fails to comply with the protocol (e.g., nonadherence to study assessment visits).
- The Investigator's judgment that continued participation is no longer in the patient's interest.

Documentation of the details of withdrawal will be included in the eCRF. All patients who receive the ¹²⁴I-PEG-AVP0458 infusion will be evaluated for safety.

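### Section 8.3.1 makes the safety population depend on a post-infusion assessment, contradicting 5.13 and 5.14; in a narrow case a dosed patient could drop out of the primary safety summaries

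*Protocol*

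**What the plan says.** Three places in the protocol say who counts for safety.

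- Section 5.13 (Patient Evaluability) says that every patient who receives the infusion of the radiolabelled "diabody will be evaluable for safety". It adds no condition.
- Section 5.14 (Criteria and rules for stopping patient treatment) ends by saying that everyone who receives the ¹²⁴I-PEG-AVP0458 "infusion will be evaluated for safety". Again there is no condition.
- Section 8.3.1 (Safety Analysis Population) adds one: "The safety analysis population includes all patients who were administered study drug and have at least one safety assessment after their infusion".

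The only other population in 8.3, the evaluable one, requires four weeks of completed assessments and is narrower still.

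Safety is the primary endpoint. Section 8.2.1 says "Safety will be evaluated by adverse events, ECOG performance status, vital signs, 12-lead ECG and laboratory parameters", and adds: "Special emphasis will be considered for any dose limiting toxic adverse event and infusion related adverse events". Section 5.9.1 counts as infusional toxicities events of Grade 2 or higher from the start of the infusion to four hours after its end. On Day 0, section 5.4 schedules vital signs "every 15 minutes during the infusion, at completion of infusion, and at 1, 2 and 4 hours after infusion completion", and section 5.3 has patients "observed for the first four hours after the infusion has been completed".

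**The concern.** For a dosed patient with no safety assessment after the infusion, the three sections cannot all be followed: 5.13 and 5.14 include the patient and 8.3.1 does not. The added condition can only remove patients, and whether a patient meets it depends on what happens after dosing begins.

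The window for infusional toxicity opens when the infusion starts, but entry to the analysis set turns on an assessment after the infusion. An acute reaction in the first minutes, which section 5.9.3 warns of, falls inside the first and before the second. At stake is whether the descriptive incidence of adverse events, in groups of three to six patients, covers everyone who was exposed.

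**Working it through.** **Step 1. The definitions side by side.**

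| Section | Received infusion | Assessment after infusion |
|---|---|---|
| 5.13 | required | not required |
| 5.14 | required | not required |
| 8.3.1 | required | required |

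The protocol does not say what qualifies as a safety assessment for 8.3.1, whether an adverse event or death record qualifies, or when the infusion ends if it was stopped early. Section 8.5 summarises adverse events by cohort and section 8.4 describes the interim safety data; neither names a population, so neither overrides 8.3.1.

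**Step 2. Which patients the two rules treat differently.**

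- Infusion completed: vital signs are due at completion and at 1, 2 and 4 hours. One reading after the end is enough, so both rules include the patient.
- Infusion stopped for a reaction, patient then observed: included under both rules, provided the later observations count as being after the infusion.
- Infusion stopped, nothing recorded afterwards: included under 5.13 and 5.14, open to exclusion under 8.3.1.
- Death during the infusion: included under 5.13 and 5.14, open to exclusion under 8.3.1 unless the event or death record counts as an assessment.

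Only the last two are exposed.

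**Step 3. The protocol's sample size.** Section 3.2 gives 12 to 18 patients. With no expansion, 3 + 3 + 6 = 12. With both escalation cohorts expanded, 6 + 6 + 6 = 18. Both ends reproduce.

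**Step 4. The group size to use.** Under sections 3.1 and 6.1 an allergic reaction of Grade 2 or higher that is at least possibly related to the drug is a DLT, and one DLT in a cohort of three adds three patients. For a single such reaction the completed escalation cohort is therefore 3 + 3 = 6. Dose group 3 also has 6. The total is 12 if the event falls in dose group 3 and neither escalation cohort was expanded, 6 + 3 + 6 = 15 if one was expanded, and 18 if both were.

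**Step 5. Effect of leaving out one patient with the event.** With x events in n patients, x/n becomes (x − 1)/(n − 1). Exact (Clopper-Pearson) 95% intervals are in brackets.

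| Setting | All infused | One patient omitted |
|---|---|---|
| Expanded cohort or dose group 3 | 1/6 = 16.7% (0.4 to 64.1) | 0/5 = 0% (0 to 52.2) |
| Total, no expansion | 1/12 = 8.3% (0.2 to 38.5) | 0/11 = 0% (0 to 28.5) |
| Total, one cohort expanded | 1/15 = 6.7% (0.2 to 31.9) | 0/14 = 0% (0 to 23.2) |
| Total, both expanded | 1/18 = 5.6% (0.1 to 27.3) | 0/17 = 0% (0 to 19.5) |

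These figures ignore replacement under section 5.15.

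**The case against.** The strongest reply is that the exclusion is possible, not certain. Section 5.4 places the during-infusion vital signs under its post-administration heading, together with the instruction "Adverse events, if observed, are recorded, taking special precaution for anaphylaxis, allergic and/or infusion reactions". Section 7.1.1 defines an adverse event as something that follows administration, so a recorded reaction or death can reasonably be taken as a safety assessment. A stopped infusion is followed by observation, and section 5.9.3 requires the event to be recorded. Patients may go home on Day 0 only without ongoing adverse effects. If 5.14 is followed for everyone infused, the definitions will normally coincide. All of this stands and makes the case rare. It does not remove the conflict, because nothing in 8.3.1 adopts that generous reading.

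Two stronger readings are tempting, and the documents do not support either.

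- A reader might infer that any patient who dies or is lost during or just after a reaction is bound to leave both numerator and denominator. Someone lost shortly after a reaction would usually already have a reading at completion or later, and the status of an event record is left open.
- A reader might infer that a cohort of three would go from 1/3 to 0/2 and that the cohort's conclusion would be lost. A drug-related allergic reaction of Grade 2 or higher expands that cohort to six. DLTs are counted among patients entered in the dose group, not in the safety population. SAEs and deaths are reported under section 7.2.2 whatever the analysis set, and section 8.5 lists adverse events by cohort.

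**Conclusion.** The contradiction between 8.3.1 and sections 5.13 and 5.14 is established by the text. Its consequence is conditional: a patient who dies during the infusion, or has no observation once it has been stopped or has ended, could be left out of the primary safety summaries. The documents do not show a systematic bias in the incidence of infusion reactions.

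If the case arose, only a descriptive percentage would change, by the amounts in the table above. This assumes that one patient has the event, that 8.3.1 is read literally, and that an event or death record is not accepted as an assessment. In a trial whose analyses are declared descriptive and exploratory this is a modest defect. It is worth correcting because safety is the primary endpoint, the groups are small, and otherwise the wording would have to be interpreted after the event was known.

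**What to change.** In section 8.3.1, delete the second condition, the one requiring a safety assessment after the infusion. Define the safety analysis population as all patients who received any amount of the ¹²⁴I-PEG-AVP0458 infusion, and state that data collected during the infusion are included. That matches 5.13 and 5.14 and settles the status of a partial or stopped infusion.

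The cost is one sentence in the protocol and the matching population flag in the data. No dose, clinical rule or sample size changes.
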